#### Visit 2 - Baseline Visit (Day 0)

The following assessments will be conducted in the order written:

- Review of concomitant medications and AEs.
- Return of acclimatisation toothpaste, toothbrush and diary.
- Review of completed diary to determine usage compliance.
- Inclusion/exclusion criteria review.
- Confirmation of subject eligibility and continuance.
- Completion of DHEQ Section 1 and Section 2.
- LMS Training Exercise
- OST examination.
- Evaporative air sensitivity assessment (Schiff Sensitivity Scale, LMS) on all eligible teeth from Visit 1.
- Selection of two test teeth.
- Dispensation of study toothpaste, toothbrush and diary.
- Supervised brushing with study treatment.
- Incidents from supervised brushing with study treatment

 GlaxoSmithKline	Document Name	Clinical Protocol 204930		
	Type	Version	Document Identifier	Effective Date
	eldo_clinical_doc	6.0; Most-Recent; Effective; CURRENT	090032d580c189ed	12-Sep-2016 05:12:55
	Reason For Issue	Auto Issue		

**Visit 3 - Week 4 (Day 28 ± 3)**  
**Visit 4 - Week 8 (Day 56 ± 3)**  
**Visit 5 - Week 12 (Day 84 ± 3)**  
**Visit 6 - Week 16 (Day 112 ± 3)**  
**Visit 7 - Week 20 (Day 140 ± 3)**

- The following assessments will be conducted in the order written:
- Review of concomitant medications, AEs and incidents.
  - Return of study toothpaste and diary. New toothbrush at Week 12.
  - Review of completed diary to determine usage compliance.
  - Confirmation of subject continuance.
  - Completion of DHEQ Section 1 (Q7-9) & Section 2.
  - OST examination.
  - Evaporative air sensitivity assessment (Schiff Sensitivity Scale, LMS) on two test teeth.
  - Evaporative air sensitivity assessment (Schiff Sensitivity Scale) on remaining eligible teeth from Visit 1.
  - Dispensation of study toothpaste and diary (and toothbrush at Visit 5).
  - Supervised brushing with study treatment.
  - Incidents from supervised brushing with study treatment

**Visit 8 - Week 24 (Day 168 ± 3)**

- The following assessments will be conducted in the order written:
- Review of concomitant medications, AEs and incidents.
  - Return of study toothpaste, toothbrush and diary.
  - Review of completed diary to determine usage compliance.
  - Confirmation of subject continuance.
  - Completion of DHEQ Section 1 (Q7-9) & Section 2.
  - OST examination.
  - Evaporative air sensitivity assessment (Schiff Sensitivity Scale, LMS) on two selected test teeth.
  - Evaporative air sensitivity assessment (Schiff Sensitivity Scale) on remaining eligible teeth from Visit 1.
  - AEs and incidents will be recorded for 5 days after last treatment.

### 3.2. Subject Restrictions

#### Lifestyle/ Dietary

- For the duration of the study (Screening – Week 24):
- Eligible subjects will be asked to stop using their regular oral care products from Screening for the duration of the study. Subjects will not be permitted to use any other oral care products (i.e., oral rinses, tongue cleaners, whitening/bleaching

 GlaxoSmithKline	Document Name	Clinical Protocol 204930		
	Type	Version	Document Identifier	Effective Date
	eldo_clinical_doc	6.0; Most-Recent; Effective; CURRENT	090032d580c189ed	12-Sep-2016 05:12:55
	Reason For Issue	Auto Issue		

products) than those provided to them. Subjects will not be permitted to use any dental products, including home remedies, intended for treating sensitive teeth.
 
 
• Subjects will be permitted to use dental floss for the removal of impacted food only.
 
• Subjects will not be permitted to chew gum.
 

Prior to study visits: (Baseline-Week 24)
 
 
• In order to standardize oral hygiene practices, subjects will be asked to refrain from all oral hygiene procedures for at least 8 hours, and from eating and drinking for at least 4 hours, prior to their scheduled Baseline and Week 4 to Week 24 visits. Within four hours of the visit (but not within one hour of the visit), small sips of room-temperature water will be permitted to take medications and relieve thirst.
 
• Subjects will be requested to refrain from excessive alcohol consumption for 24 hours prior to the Baseline and all subsequent visits. If, in the opinion of the Investigator, the subject has consumed an excessive amount of alcohol prior to a visit, every effort will be made to reappoint them to the next day. If this is not possible, the subject should be treated as per section 4.4.
 

Medications and Treatments


For the duration of the study (screening – last visit):
 
 
• If concomitant medications and traditional herbal ingredients/treatments are used during the study, their identity, as well as their dosage and frequency, start and stop dates must be recorded in the CRF.
 
• Should a subject take an analgesic within 8 hours of a scheduled visit, every effort will be made to reappoint them to the next day. If this is not possible, the subject should be treated as per section 4.4.
 
• Subjects who enter the study will be requested to delay having any non-emergency, elective dental treatment until after study completion (including dental prophylaxis).
 

### 3.3. Type and Planned Number of Subjects

Approximately 200 subjects will be screened to ensure approximately 112 suitable subjects enter the acclimatisation phase. Approximately 75 eligible subjects will be allocated the study toothpaste in order to ensure that approximately 60 subjects complete the study.

Subjects will be recruited by the CRO, primarily from their volunteer database. Subjects may also be recruited via advertisements placed in the local press, by use of leaflets and posters or by word of mouth.

 GlaxoSmithKline	Document Name	Clinical Protocol 204930		
	Type	Version	Document Identifier	Effective Date
	eldo_clinical_doc	6.0; Most-Recent; Effective; CURRENT	090032d580c189ed	12-Sep-2016 05:12:55
	Reason For Issue	Auto Issue		

### 3.4. Study Design and Dose Justification

The current study will explore the impact of long term management of DH with daily use of a sensitivity toothpaste on the quality of life of a population of sensitivity sufferers, using the DHEQ. Changes in DH will also be monitored clinically over the 24 week treatment period.

A non-comparative, monadic study design has been selected as appropriate to achieve the aims of this research. The inclusion of a control or comparator treatment is not considered necessary to meet the objectives of the study (which is to monitor To monitor the impact of long term management of DH over a 24 week period, with twice daily use of a sensitivity toothpaste, on the oral health related quality of life in sensitivity sufferers, as measured by the DHEQ). All subjects will use the same sensitivity toothpaste (a clinically proven 0.454% w/w stannous fluoride formulation [GSKCH Study RH01685; Parkinson, 2013] for the duration of the 24 week study period.

The anti-sensitivity efficacy of toothpastes containing 0.454% w/w stannous fluoride has been established in a number of published studies [for example Schiff, 2000a, 2000b, 2006a; Pradeep, 2010; Sharma, 2010; Chaknis, 2011; Du, 2011; Ni, 2011; Parkinson, 2013]; and will not be investigated further here. The study toothpaste contains 0.454% stannous fluoride and will be provided in commercial tubes, overwrapped to mask its identity. The dosage regimen of twice daily brushing (morning and evening) will be the same for all subjects, and has been selected based on dental health care professionals (DHCP) recommended practice.

It is anticipated that DH symptoms will decrease over the 24 week study period with daily use of a clinically proven, sensitivity toothpaste. A validated, condition specific measure of oral health-related quality of life for DH (Dentine Hypersensitivity Experience Questionnaire (DHEQ) [Boiko, 2010; Baker, 2014] will be completed by the subjects at Baseline and 4, 8, 12, 16, 20 and 24 weeks to monitor the impact of a reduction in DH on everyday life. The DHEQ (48 item) has been shown to have good psychometric properties in both the general population, and in DH sufferers [Boiko, 2010; Baker, 2014].

An evaporative air stimulus will be administered using a dental air syringe. Response to this stimulus will be evaluated using

- Schiff Sensitivity Scale [Schiff, 1994]: This is an examiner assessment of the subject's response to an evaporative air stimulus. It is scored immediately following the stimulus and focuses on a combination of specific, observable, physical, behavioural and verbal responses from the subject as a result of the

	Document Name	Clinical Protocol 204930		
	Type	Version	Document Identifier	Effective Date
	eldo_clinical_doc	6.0; Most-Recent; Effective; CURRENT	090032d580c189ed	12-Sep-2016 05:12:55
	Reason For Issue	Auto Issue		

stimulation of exposed dentine, rather than solely an oral request from the subject to discontinue stimulation and may facilitate discrimination.

- Labelled Magnitude Scales (LMS) [Heaton, 2013]: These are completed by the subject following the evaporative stimulus (on a tooth by tooth basis) and apply psychophysical procedures (magnitude estimation and cross-modality magnitude matching) to condition specific descriptive words relevant to the subject's response. The descriptive words are then aligned along a Visual Analogue Scale (VAS) at distances that reflect the psychological distances between words. These scales have been piloted and validated in a previously reported dentine hypersensitivity trial.

The selection of two 'test teeth' to evaluate changes in DH is common practice in sensitivity studies [Docimo, 2009]. The sensitivity of the remaining teeth that qualified following assessments of EAR, MGI and tooth mobility at Screening will also be assessed at Baseline and 4, 8, 12, 16, 20 and 24 weeks.

The dosage regimen of twice daily usage (morning and evening) for 1 timed minute will be the same for all subjects, and has been selected based on widely recommended oral hygiene practice, and typical consumer habit.

## 4. SELECTION OF STUDY POPULATION AND WITHDRAWAL CRITERIA

Specific information regarding warnings, precautions, contraindications, adverse events, and other pertinent information on the GSK investigational product or other study treatment that may impact subject eligibility is provided in the Safety Statement.

Deviations from inclusion and exclusion criteria are not allowed as they can potentially jeopardize the scientific integrity of the study, regulatory acceptability or subject safety. Therefore, adherence to the criteria as specified in the protocol is essential.

### 4.1. Inclusion Criteria

A subject will be eligible for inclusion in this study only if all of the following criteria apply:

1. CONSENT
Demonstrates understanding of the study and willingness to participate as evidenced

-

 GlaxoSmithKline	Document Name	Clinical Protocol 204930		
	Type	Version	Document Identifier	Effective Date
	eldo_clinical_doc	6.0; Most-Recent; Effective; CURRENT	090032d580c189ed	12-Sep-2016 05:12:55
	Reason For Issue	Auto Issue		

by voluntary written informed consent and has received a signed and dated copy of the informed consent form.

## 2. AGE

Aged 18-55 years.

## 3. GENERAL HEALTH

Good general and mental health with, in the opinion of the investigator or medically qualified designee:

- a) No clinically significant and relevant abnormalities of medical history or oral examination.
- b) Absence of any condition that would impact on the subject's safety or wellbeing or affect the individual's ability to understand and follow study procedures and requirements.

## 4. COMPLIANCE

Understands and is willing, able and likely to comply with all study procedures and restrictions.

## 5. DENTAL HEALTH

### *At Visit 1 (Screening):*

- a) Self-reported history of dentinal hypersensitivity (DH) lasting more than six months but not more than 10 years.
- b) Minimum of 20 natural teeth.
- c) Minimum of 2 accessible non-adjacent teeth (incisors, canines, pre-molars), preferably in different quadrants, that meet all of the following criteria:
  - Signs of facial/cervical gingival recession and/or signs of erosion or abrasion (EAR).
  - Tooth with MGI score =0 adjacent to the test area (exposed dentine) only [Lobene, 1986] and a clinical mobility of  $\leq 1$
  - Tooth with signs of sensitivity measured by qualifying evaporative air assessment (Y/N response)

### *At Visit 2 (Baseline):*

- d) Minimum of two, non-adjacent accessible teeth (incisors, canines, pre-molars), that meet all of the following criteria:
  - with signs of sensitivity, measured by a qualifying evaporative air assessment (Schiff Sensitivity Score  $\geq 2$ )

Note: All teeth which meet the EAR, GI and mobility inclusion criteria and none of the dentition exclusion criteria at Screening should be assessed by

 GlaxoSmithKline	Document Name	Clinical Protocol 204930		
	Type	Version	Document Identifier	Effective Date
	eldo_clinical_doc	6.0; Most-Recent; Effective; CURRENT	090032d580c189ed	12-Sep-2016 05:12:55
	Reason For Issue	Auto Issue		

evaporative air stimulus at Baseline. *Test Teeth* should not be adjacent to each other and preferably in different quadrants.

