## 2. OBJECTIVES AND ENDPOINTS

Objectives	Endpoints
Primary	
To monitor the impact of long term management of DH over a 24 week period, with twice daily use of a sensitivity toothpaste, on the oral health related quality of life in sensitivity sufferers, as measured by the DHEQ.	Change from baseline in DHEQ endpoints over time.
Exploratory	
To evaluate changes in dentine hypersensitivity over the 24 week treatment period, including the number of sensitive teeth, as measured by Schiff Sensitivity Score to assess examiner performance on this measure.	
Mean Schiff Sensitivity Score for all timepoints.
 
Change from baseline in Schiff sensitivity score (two test teeth) for all timepoints.
 
Change from baseline in Schiff sensitivity score (all qualifying teeth) for all timepoints.

To evaluate changes in dentine hypersensitivity over the 24 week treatment period, as measured by Labelled Magnitude Scales (LMS).	At each time point the mean LMS (of each of 4 VAS scales) and change from baseline (for the two test teeth) and will be calculated.

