#### 6.1.7.4. Qualifying Evaporative air Sensitivity

The screening dentist will assess sensitivity by a simple air blast on the facial surface of all teeth that meet the EAR, MGI and mobility criteria. This assessment is made by directing a one second application of air from a standard dental syringe perpendicular to the tooth surface approximately 1- 2 mm coronal to the free gingival margin and from a distance of approximately 1cm. Following the air blast, the dentist will ask the subject if they experienced sensitivity. In order to qualify, the subject should confirm they experienced sensitivity and a simple “yes/no” response will be recorded.

## 6.2. Visit 2 to Visit 8

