### 6.2.4. Evaporative Air Sensitivity Assessments

This assessment will be conducted by a single examiner for all subjects at each visit by directing a maximum one second application of air from a dental air syringe to the exposed dentine surface from a distance of approximately 1 cm. The examiner should take appropriate measures to isolate the test tooth surface in order to prevent stimulus exposure to adjacent tooth or surrounding soft tissue.

At Baseline, the examiner will assess the evaporative air sensitivity of all clinically eligible teeth identified at Screening (teeth that qualified on EAR, MGI and tooth mobility criteria, and had none of the dentition exclusions), using the Schiff

	Document Name	Clinical Protocol 204930		
	Type	Version	Document Identifier	Effective Date
	eldo_clinical_doc	6.0; Most-Recent; Effective; CURRENT	090032d580c189ed	12-Sep-2016 05:12:55
	Reason For Issue	Auto Issue		

Sensitivity Scale and LMS (Appendix 4). Two test teeth will be selected according to specific eligibility criteria in an individual subject.

At Week 4, 8, 12, 16, 20 and 24 visits the examiner will first assess the evaporative air sensitivity of the two identified test teeth from the Baseline visit using the Schiff Sensitivity Scale and LMS. The examiner will then assess the evaporative air sensitivity of the remaining Eligible Teeth from Screening (teeth that qualified on EAR, MGI and tooth mobility criteria, and had none of the dentition exclusions), using the Schiff Sensitivity Scale.

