## 8.2 Exploratory Analyses

The following exploratory analyses will be conducted.

At each time point the mean Schiff Sensitivity Score (for the two test teeth and all qualifying teeth) and mean LMS scores [each of 4 scales (description, tolerability, description, intensity)] as well as the change from baseline will be calculated.

 GlaxoSmithKline	Document Name	SAP 204930.doc		
	Type	Version	Document Identifier	Effective Date
	eldo_clinical_doc	1.0; CURRENT; Most-Recent; Effective	090032d580cb2f1e	10-Nov-2016 09:05:48
	Reason For Issue	Auto Issue		

The above each endpoint will be analysed using mixed effect ANOVA with visit and site as fixed effect, subject as random effect. Adjusted Means will be computed for each visit. Using this model, the post baseline visit will be compared to the baseline visit and difference of their effect will be computed along with P-values and 95% confidence interval.

The visit by site interaction will be investigated by including the visit by site interaction term. If the visit by site interaction term is not significant at the 10% level of significance then this term will be removed from the model.

If the visit site interaction term is significant at 10% level of significance then the interaction will be included in the model and all model estimates (Adjusted Means, 95% CIs and P-values) for within and between visits will be reported separately for each site and based on results from visit by site interaction.

Standard summary measures, 95% CIs and p-values will be presented. A plot of means of raw scores over time (mean  $\pm$  standard errors) will also be presented for all measures.

The assumption of normality and homogeneity of variance in the ANOVA model will be investigated. Violation of these assumptions may be overcome using suitable transformation or performing a non-parametric test (e.g., the Wilcoxon signed-rank test).

The percentage of teeth that are sensitive (Schiff sensitivity score  $>0$  of all qualifying teeth from screening (termed 'the qualifying teeth') will be summarised for each timepoint and also plotted over time.

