[1] Baseline only includes those subjects who have a corresponding post-baseline assessment. Baseline = Day 0.

[2] From mixed effect ANOVA model with visit and site as fixed effect, subject as random effect.

[2] Difference is first named week minus second named week such that a positive difference favors the first named week.

CFB= Change From Baseline;

PPD

PPD

Programming note: Same tables will be populated for- 'Week 12', 'Week 16', 'Week 20' and 'Week 24'. Please repeat tables for the Q8 and Q9.

 GlaxoSmithKline	Document Name	SAP 204930.doc		
	Type	Version	Document Identifier	Effective Date
	eldc_clinical_doc	1.0: CURRENT, Most-Recent, Effective	090032d580cb2f1e	10 Nov 2016 09:05:48
	Reason For Issue	Auto Issue		

Protocol: 207238

Program Run Date: DDMMYYYY

Table 9.3.2.1  
 Summary Statistics of Evaporative (Air) Sensitivity (Schiff Sensitivity Score) By Site and Overall  
 Intent to Treat Population

Study Population: Intent to Treat Population (N=XXX)

TWO TEST TEETH	SITE 1 (N=XX)	SITE 2 (N=XX)	OVERALL (N=XX)
BASELINE			
N (NON-MISSING)	XXX	XXX	XXX
MEAN	X.XXX	X.XXX	X.XXX
SD	X.XXX	X.XXX	X.XXX
SE	XX.X	XX.X	XX.X
MEDIAN	XX.X	XX.X	XX.X
MINIMUM	XX.X	XX.X	XX.X
MAXIMUM	XX.X	XX.X	XX.X
WEEK 4			
N (NON-MISSING)	XXX	XXX	XXX
MEAN	X.XXX	X.XXX	X.XXX
SD	X.XXX	X.XXX	X.XXX
SE	XX.X	XX.X	XX.X
MEDIAN	XX.X	XX.X	XX.X
MINIMUM	XX.X	XX.X	XX.X
MAXIMUM	XX.X	XX.X	XX.X
WEEK 8...			
PPD		PPD	

Programmer note: Please repeat same table for all qualifying teeth.

	Document Name	SAP 204930.doc		
	Type	Version	Document Identifier	Effective Date
	eldo_clinical_doc	1.0: CURRENT: Most Recent: Effective	090032d580cb2f1e	10 Nov 2016 09:05:48
	Reason For Issue	Auto Issue		

Protocol: 204930

Program Run Date: DDMMYYYY

Table 9.3.2.2

Summary and Statistical Analysis of Measures of Dentinal Hypersensitivity (Schiff Sensitivity Score) Over Time

Study Population: ITT (N=XX)

TWO TEST TEETH								
	BASELINE	BASELINE [1]	WEEK 4 VALUES	CFB [1]	BASELINE [1]	WEEK 8 VALUES	CFB [1]	
N	XX	XX	XX	XX	XX	XX	XX	XX
MISSING	XX	XX	XX	XX	XX	XX	XX	XX
MEAN	X.XX	X.XX	X.XX	X.XX	X.XX	X.XX	X.XX	X.XX
SD	X.XXX	X.XXX	X.XXX	X.XXX	X.XXX	X.XXX	X.XXX	X.XXX
SE	X.XXX	X.XXX	X.XXX	X.XXX	X.XXX	X.XXX	X.XXX	X.XXX
MEDIAN	X.X	X.X	X.X	X.X	X.X	X.X	X.X	X.X
MINIMUM	XX	XX	XX	XX	XX	XX	XX	XX
MAXIMUM	XX	XX	XX	XX	XX	XX	XX	XX
ADJUSTED MEAN [2]			XX.XX			XX.XX		
95 % CIS [2]			[X.XX, X.XX]			[X.XX, X.XX]		
P-VALUES [2]			0.XXXX			0.XXXX		

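### One Visit 2 Schiff score both selects the two test teeth and serves as their baseline, so the test-tooth change is biased downward and its p-values are not valid tests of no change

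*Protocol*

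**What the plan says.** **Selection.** Criterion 5(d) in Protocol 4.1 asks for at least two non-adjacent teeth "with signs of sensitivity, measured by a qualifying evaporative air assessment (Schiff Sensitivity Score" ≥ 2). Protocol 6.2.4 describes the Visit 2 reading: "At Baseline, the examiner will assess the evaporative air sensitivity of all clinically eligible teeth identified at Screening". It then states: "Two test teeth will be selected according to specific eligibility criteria in an individual subject". The Visit 2 lists in the synopsis and Section 3.1 place test-tooth selection directly after this assessment. No rule is given for choosing when more than two teeth reach 2.

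**No other pre-treatment Schiff score.** The Screening air test (6.1.7.4) is graded yes or no: "In order to qualify, the subject should confirm they experienced sensitivity".

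**Analysis.** One exploratory endpoint is: "Change from baseline in Schiff sensitivity score (two test teeth) for all timepoints". The table templates in SAP Appendix 3 fix the reference: "Baseline = Day 0". SAP 8.2 takes its 95% intervals from a "mixed effect ANOVA with visit and site as fixed effect, subject as random effect" and says of the contrasts: "the post baseline visit will be compared to the baseline visit and difference of their effect will be computed along with P-values". Schiff over all qualifying teeth gets the same treatment, with nothing to distinguish the two results.

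**Design.** Protocol 3.4 explains that no control is included. Neither document mentions regression to the mean.

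**The concern.** A single air blast per tooth does two jobs at Visit 2: it admits the tooth because it scored 2 or 3, and it supplies the value from which change is measured. Any measurement error in that score is, on average, upward in the chosen teeth. The error does not recur at Week 4, so the mean drops whatever the toothpaste does.

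A concurrent control would show the same drop, and it would cancel in the comparison. Here nothing cancels it. The p-values for test-tooth Schiff therefore test a null hypothesis that the selection step has already made false.

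At stake is the exploratory objective of evaluating change in hypersensitivity over 24 weeks. There is also an indirect effect: Protocol 3.4 says the DHEQ is there to monitor the impact of a reduction in hypersensitivity, and the test-tooth Schiff result is a natural place to look for evidence that such a reduction occurred.

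**Working it through.** **The plan's own figures.** None is given for Schiff or LMS. The stated power (60 completers, at least 90%, two-sided 5%) concerns DHEQ. It cannot be reproduced, because no mean change or SD is given. It would need mean change/SD of at least 0.425. The allocation is consistent with 20% dropout: 60 / (1 − 0.20) = 75. I take n = 60 from here.

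**Rough size by hand.** With reliability r, the expected fall is about (1 − r) × (mean of selected teeth − mean of all eligible teeth). Assume 15/30/35/20% of teeth score 0/1/2/3.

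- All eligible teeth: 0.30 × 1 + 0.35 × 2 + 0.20 × 3 = 1.60.
- Teeth scoring 2 or 3: (0.35 × 2 + 0.20 × 3) / 0.55 = 2.364.
- Gap: 0.764. With r = 0.7, the fall is about 0.3 × 0.764 = 0.23 points.

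The simulation below gives 0.31 for this case. It is larger mainly because r there refers to the underlying continuous response, and cutting that into four grades makes the score less repeatable.

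**Simulation with no true change.**

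- From the documents: 0–3 scale, entry with at least two teeth scoring 2 or more, Baseline plus six visits, n = 60, random-intercept model, two-sided 5%.
- Assumed: reliability 0.5 to 0.95; six eligible teeth per subject; half of the true variance between subjects; two qualifying teeth taken at random; independent visit errors; three score distributions (15/30/35/20%, 5/20/45/30% and 30/30/25/15%).
- Site and the non-adjacency rule are left out.
- Test: mean change divided by √(2 × MSE / 60), on 59 × 6 = 354 degrees of freedom; 400 trials per scenario.

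Test-tooth Schiff, Week 24 against Baseline, range over the three distributions:

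| Assumed reliability | Mean change | Trials with a significant fall |
|---|---|---|
| 0.5 | −0.25 to −0.67 | 92–100% |
| 0.7 | −0.17 to −0.44 | 76–100% |
| 0.8 | −0.13 to −0.33 | 63–99% |
| 0.9 | −0.09 to −0.20 | 51–94% |
| 0.95 | −0.06 to −0.13 | 37–77% |

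With perfect reliability, the change is zero. A significant fall at one or more of the six visits occurs in 79% to 100% of trials. A further simulation over the same reliability range widens the span to a fall of 0.06 to 0.80 points and rejection in 28% to 100%.

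**Is selection the cause?** When a second reading that played no part in selection serves as baseline, the mean change lies between −0.005 and +0.006 and rejection is 3.7% to 6.0%.

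**Other contrasts, also with no true change.**

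- *All qualifying teeth:* change of −0.004 to −0.094 and rejection of 4.5% to 35.5% in the tabulated scenarios; 3% to 62% in the further simulation. Some bias remains because subjects enter on the same scores.
- *Week 4 to Week 24, test teeth:* rejection of 2% to 8% if visit errors are independent. If Baseline and Week 4 errors correlate at 0.4, there is a fall of 0.05 to 0.22 points and rejection in 13% to 50%.
- *Eligible teeth not chosen as test teeth:* a rise of 0.02 to 0.33 points and rejection in 10% to 96%, because high scorers have been removed.
- *LMS on the test teeth:* the result turns on how far its error correlates with the Schiff error. At reliability 0.7 and the 15/30/35/20% distribution, a significant fall occurs in 2.5% of trials (the nominal one-sided rate) at correlation 0, 17% at 0.3, 47% at 0.6 and 86% at 0.9.

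**The case against.** The best defence is that little rests on this result. Schiff and LMS are exploratory, and the Schiff objective is partly about examiner performance. Protocol 3.4 says anti-sensitivity efficacy will not be investigated further, 9.2.4 sets no formal success criteria, and the SAP's topline tables (Section 11) contain no Schiff or LMS output. Schiff over all qualifying teeth is already planned. All of this stands, and it limits how much the point matters. It does not make the planned p-values valid.

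Protocol 3.4 also calls two test teeth common practice. The study it cites is, by its title, a comparison of two toothpastes, where a shift shared by both arms cancels. That precedent does not carry over to a single-arm study.

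A reader might go further in three ways that the documents do not support.

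- *A significant fall is certain.* This depends on Schiff reliability, the score distribution and the number of eligible teeth, none of which is given.
- *LMS is biased as well.* LMS is rated after the same stimulus and, after Baseline, only on the test teeth, but it does not select them. The link between its error and Schiff's is unknown.
- *The primary analysis is undermined.* DHEQ is not the selection variable, and nothing shown here reaches it.

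**Conclusion.** The point holds for Schiff on the two test teeth. The documents alone establish the downward bias: the selecting score is the baseline, no second pre-treatment score exists and there is no control arm. Only the size rests on assumptions. With reliability of 0.5 to 0.95, it is about 0.06 to 0.8 points, and the planned test against baseline rejects in about 28% to 100% of trials with no true change, against a nominal 5%. For LMS a caution is warranted, not a finding of bias. The consequence is confined to exploratory endpoints; neither the DHEQ analysis nor the sample size is affected by this argument.

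**What to change.** Amend SAP 8.2 and Tables 9.3.2.2 and 9.3.3.2:

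1. Make Schiff over all qualifying teeth the lead Schiff measure, with a footnote that a smaller bias from subject entry remains.
2. For the two test teeth, report Schiff change from baseline descriptively, without p-values offered as evidence of change. Footnote that the baseline score was also the selection score. Add a caution to the LMS table that its baseline may be affected if LMS and Schiff errors are correlated.
3. Add the Week 4 to Week 24 test-tooth contrast from the same model. State that it is free of the selection effect only if visit errors are independent, and that it leaves out change in the first four weeks.

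Do not add a row for eligible teeth that were not chosen. It would be biased in the opposite direction, and it would be empty for a subject with only the minimum two eligible teeth.

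The cost is SAP wording, footnotes and one extra contrast, with no new data. The downside is a less impressive test-tooth result. A second Baseline reading not used for selection would be cleaner, but the protocol does not collect one, so that is a matter for a future design.
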